1. Concurrent (within the last three week period before PEP administration) use of medication not present on the 'safe' list

Remarks regarding PEP distribution:

- Children between 2 and 5 years of age or weighing between 10 and 20 kg or people taking medication from the unsafe list will be excluded from BE-PEP and offered SDR-PEP if eligible.
- Study participants living in the PEP zone but ineligible for PEP due to the PEP inclusion or exclusion criteria or being absent during the village PEP distribution round will not be automatically included in the PEP distribution the following year. It is possible that a study participant is not eligible one year due to the PEP inclusion or exclusion criteria but will be eligible for PEP the next year when the household is again part of the newly calculated PEP zone and the individual inclusion or exclusion criteria are respected.
- Household contacts of an index case in the BE-PEP arm absent during the 1st annual PEP distribution but present during the 2nd annual PEP distribution will only be offered PEP once that year and will not be revisited after 30 days.
- Participants who are not BE-PEP eligible due to concomitant medication not present on the 'safe list' can be provided SDR-PEP, provided they do not meet any other exclusion criteria.
- Children who are not BE-PEP eligible solely for not meeting age and weight criteria, can be provided SDR-PEP if aged 2 years or above and weighing 10 kg or above.

All leprosy patients diagnosed during the study period, even those from non-study villages, will also be enrolled in a sub-study in which potentially a nasal/tongue swab, a tongue scraping sample, face mask sample and skin biopsies will be collected from non-facial lesions. qPCR on these samples will allow to verify the accuracy of the clinical diagnosis and further processing with Deeplex Myc-Lep V3 of qPCR positive samples (or WGS if needed), will allow to monitor drug resistance and assess the impact of the intervention on transmission of *M. leprae*. As drug resistance may also affect treatment for tuberculosis, we will also sample all GeneXpert positive tuberculosis patients identified on Anjouan, Mohéli, and Grande Comore during the study period for drug resistance testing with Deeplex Myc-TB XL, and verify whether they received rifampicin and/or bedaquiline in the past.

4.3 Sample size

The sample size for the phase 2 trial is based on non-inferiority of the BE-PEP regimen compared to the SDR-PEP regimen in terms of adverse events, in particular QTc prolongation. We assume that in the SDR group the mean QTc will be equal to that of a reference population, i.e. 384 ms (SD 20 ms) based on the Fridericia correction method. [29]

The sample size calculations were performed by simulation, in a scenario where there is truly no difference between the standard and experimental treatment. A sample size of 64 patients are required per arm to achieve 80% power in the comparison that the upper limit of a one-sided 95% confidence interval will be below the non-inferiority limit of +10 ms.

For this part of the trial we have selected a village with a total recorded population of 908, 51% of whom are aged 18 years or above. As explained in chapter 4.2 above, as a matter of precaution we will first enroll adults and preliminarily assess their outcomes before we will start enrolling minors. The numbers of adults to be enrolled will be proportional to the observed age distribution at the time of the 2022 survey. To arrive at an accurate estimate of mean QTc for adults as well as for minors, we will recruit 150 participants per study arm, approximately 75 adults and 75 minors.

Overall, all ages combined, our intended sample size of 150 in each arm, which will provide 99% power to show that the upper limit of a one-sided 95% confidence interval will be below the non-inferiority limit of +10ms, assuming that in the larger population QTc does not differ between those receiving SDR-PEP and those receiving BE-PEP. Sample size calculations were done in R version 4.0.2.[30]

To calculate the sample size required for the phase 3 trial, with the main objective of assessing the impact of BE-PEP versus SDR-PEP on leprosy risk at individual level, we used the methodology described by Hayes and Bennet for cluster randomized trials.(10) Our aim is to show a 50% reduction in risk of leprosy over a 3-year period for those that received BE-PEP (arm 1) compared to those that received SDR-PEP (arm 2). We assume that in the latter arm the risk over a 3-year period will be 0.0033, i.e. 1.1 per 1,000 per year. The mean population size of the villages targeted is 2,819, however children below 5 years of age or weighing below 20 kg are not eligible for BE-PEP and make up 27% of the population. Even though part of them will be eligible for SDR-PEP, we will exclude them from this analysis because the risk of leprosy varies with age. We will therefore only compare individuals aged 5 years or above and weighing 20 kg or above. We also took into account the participation rate, i.e. the proportion of eligible participants that agreed to take PEP, which in the PEOPLE trial was 83%. Thus on a population of 2,850, only 1,708 will effectively be available for analysis. For the PEOPLE trial we calculated a coefficient of variation between clusters (km) of 0.34, in the BE-PEOPLE trial we assume a slightly higher Km, 0.4. To achieve a power (1- β) of 90% with an average cluster size of 1,708 and $\alpha = 0.05$, 22 clusters per study arm would be required, i.e. 75,152 subjects for the two arms combined. To enroll 75,152 eligible subjects we need to target a population of approximately 124,000 in total. We therefore selected 43 villages with a total population of 124,035, of which one will be divided into two clusters.

Of the 43 villages selected, 34 are already enrolled in the PEOPLE trial with a total population of approximately 73,000. In addition we have selected 9 new villages with an estimated available population of 51,000. For the new villages we have assumed a coverage of 50% only as they are large villages and we will exclude the neighborhoods from which leprosy patients are seldom reported.

For the secondary objective of assessing the effect of BE-PEP at village level, the entire population examined will be considered in the analysis. If incidence at village level is 1.1 per 1,000 per year, as observed in the PEOPLE trial, and a 50% reduction is achieved with BE-PEP, the available sample size would provide a power of approximately 90% over a three-year follow-up period.

For the surveillance for resistance in tuberculosis patients, with the Deeplex Myc-TB XL, we will include all microbiologically confirmed TB patients on the three islands of Comoros, and request samples that may include tongue and nasal swabs, in addition to sputum. Annually 50-60 such patients are being reported in recent years. Elsewhere, minority bacterial populations with mutations in *M. tuberculosis* gene *Rv0678*, an efflux pump regulator, which can give low level bedaquiline resistance, have sporadically been found in patients and populations never exposed to bedaquiline or clofazimine. We therefore will do this surveillance throughout BE-PEOPLE phase 3, also include as controls TB patients identified in Grande Comore, where bedaquiline is not used.

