respective village has been completed. For the first PEP distribution round in 2023, any leprosy case recorded during the first village screening that year or in the preceding five-year period, i.e. since January 1st, 2018, will be considered an index case. As of the 2nd annual screening round, any leprosy case detected after the screening of the previous year and up to and including the village's screening round of the current year will be considered an 'index case'. First eligibility at household level will be determined based on the distance of the household to the closest index case (Eligibility based on PEP zone). In both arms we will target anyone living within 100 meters of an index case or the entire village if more than 50% of the population are eligible. Afterwards the eligible households will be visited and individual inclusion and exclusion criteria for the annual PEP distribution will be checked before offering PEP to a study participant. Provision of PEP will start in 2023 and follow-up will continue for 4 years. Our main study outcome will be the comparison of leprosy risk in individuals that received standard WHO SDR-PEP versus individuals that received BE-PEP. In addition, we will compare the overall leprosy incidence over the follow-up period between the two study arms.

As stated above, our primary outcome measure will be the incidence rate ratio of leprosy between those who received BE-PEP and those who received the standard SDR-PEP. From this analysis we will exclude those not eligible for BE-PEP, i.e. children below 5 years of age and/or with a weight below 20 kg. We will fit a Poisson model with village nested in island as random effect and controlled for distance to the nearest index case at baseline. In addition, we will compute compare the incidence rate ratios between the entire BE-PEP and SDR-PEP arms over a period of 4 years starting at the first screening round up to the last follow up after 4 years, also based on a Poisson model with village nested in island as random effect. From this analysis we will not exclude anyone not eligible for BE-PEP.

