Year 2	Phase 3 study	Screening Arm 1 & 2 + PEP intervention	Sampling leprosy patients	Sampling TB patients	
Year 3	Phase 3 study	Screening Arm 1 & 2 + PEP intervention	Sampling leprosy patients	Sampling TB patients	
Year 4	Phase 3 study	Final screening Arm 1 & 2	Sampling leprosy patients		PGL-I survey

Table 1: Time table BE-PEOPLE

Participants in the new villages will be asked for informed consent for baseline screening in 2022. Informed consent for the phase 3 intervention trial will be asked during the first intervention round in 2023, when we know to which study-arm villages have been randomized. Informed consent for the leprosy patient cohort will remain separate, the same applies to the TB patients being enrolled. For the PGL-I survey in 2026, separate informed consent will be asked ahead of the survey.

Figure 1 below shows how villages belonging to the various arms of PEOPLE will merge into BE-PEOPLE. We have dropped some villages that had a low incidence so far during the PEOPLE trial or a small population size. To arrive at the required sample size we will also include nine new villages, eight on Anjouan and one on Mohéli, the latter to be split into two clusters. Villages will be arranged by PEOPLE study arm and by island in order of decreasing prevalence during the 2022 baseline survey and regrouped into pairs. Within each pair they will be randomized to arm 1 or arm 2 of BE-PEOPLE.

[figure not shown]

Figure 1: Inclusion and randomization BE-PEOPLE (Phase 3) trial

The main outcome measure of BE-PEOPLE will be the incidence rate ratio of leprosy between individuals in arm 1 who received BE-PEP and individuals in arm 2 who received SDR-PEP, controlled for potential confounding by distance to nearest index case at baseline, as well as for contextual confounding through the use of a random effects model (village nested within island). To avoid a potential selection bias, those who received SDR-PEP but would not have been eligible for BE-PEP, i.e. children below the age of 5 or with a weight below 20 kg, will be excluded from this analysis. Details are described in chapter 9, 'Data analysis'.

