9. STATISTICAL ANALYSIS

The statistical analysis will be described in the statistical analysis plan (SAP), written by the biostatistician, which is binding and will be finalized before database lock or before any other analysis takes place.

9.1 Baseline characteristics:

Both an intention to treat (ITT) and a per-protocol (PP) approach will be used to define the analysis populations in both phase 2 and phase 3 studies. In the Intention-to-Treat analysis, all participants will be analyzed according to their randomized allocation, even in case they do not receive the randomized treatment, show protocol violations prior to or during the study.

In the per-protocol analysis only participants who received PEP as planned, have completed follow-up, and follow the protocol as planned are included.

In the phase 2 study, the PP population will be the primary analysis population as indicated for non-inferiority studies by the ICH-E9 guidelines. For the phase 3 study, the intention to treat will be the primary approach.

The number of participants screened and enrolled or excluded will be summarized according to reason for exclusion. Of the enrollees, the number of patients discontinued or lost to follow-up will be recorded by reason and time of discontinuation. These figures will be summarized in a CONSORT flow diagram.

Subjects in each treatment group will be described according to baseline characteristics. The description will be in terms of medians and interquartile ranges for continuous variables and using counts and percentages for categorical variables. Standard statistical tests of significance of imbalance in baseline characteristics will be performed.

9.2. Phase 2 study:

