9.3. Phase3 study

9.3.1. Primary analysis

The main analysis will be to assess the effect of BE-PEP at individual level. Because in the first study year anyone living within 100 meter of an index case over the period 2018-2023 will be eligible for PEP and if this is more than 50% of the village population the entire village population above 2 years of age will be eligible where for the first year any leprosy case included in the study population detected

during the annual village screening or in the preceding five-year period, i.e. since January 1st, 2018 will be considered an index case. The following years, any leprosy case detected after the last year's screening up to and including the village's screening round of the current year will be considered an index case. Therefore, we assume that in the first year there will be blanket coverage with either SDR-PEP or BE-PEP. We will fit a Poisson model adjusted for follow-up time as an offset term with village nested in island as random effect and type of PEP (BE-PEP or SDR-PEP), as explanatory variable. Those who did not receive PEP and those below the age or weight limits for BE-PEP will be excluded from this analysis, SDR-PEP will be our reference category. Outcome variable will be incident leprosy. We will consider all cases diagnosed after the first intervention round in 2023, until the final survey in 2026.

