11. DATA MANAGEMENT

In the BE-PEOPLE study for the baseline survey we will continue to use formats developed in the PEOPLE study consisting of a paper survey form, three forms in an Android app and an Access database with barcode, name, age and gender of each participant enrolled. After the baseline survey in 2022, which partly overlaps with the final survey of PEOPLE, we will shift from ODK Collect used in the PEOPLE trial to REDCap, which is GCP compliant. REDCap will also be used in the phase 2 study in 2022.

Data Management will be performed by the CTU data managers in collaboration with the Principal Investigator and with the study staff involved in collecting and handling the study data. The continued follow-up of the cohort of leprosy patients established during the PEOPLE trial and the preceding ComLep trial, of which drug resistance surveillance is a part, we also shift to REDCap. Drug resistance surveillance will be extended to tuberculosis patients, data collection for this part will also be integrated in the REDCap database.

A separate Data Management Plan will be prepared, with following essential aspects:

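### The phase 3 primary model compares PEP recipients without adjusting for age, although the protocol says leprosy risk varies with age

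*Protocol*

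**What the plan says.** Protocol section 9.3.1 specifies a Poisson model with follow-up time as offset, "with village nested in island as random effect and type of PEP (BE-PEP or SDR-PEP), as explanatory variable". It has no other fixed effect. The synopsis and section 3.1 add one covariate: "We will fit a Poisson model with village nested in island as random effect and controlled for distance to the nearest index case at baseline" and "controlled for potential confounding by distance to nearest index case at baseline". None of the three mentions age or sex.

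The analysis set is recipients only: "Those who did not receive PEP and those below the age or weight limits for BE-PEP will be excluded from this analysis". Section 4.3 explains the age and weight restriction by saying "we will exclude them from this analysis because the risk of leprosy varies with age"; section 3.1 gives avoidance of selection bias as the reason. Section 9.1 nevertheless states: "For the phase 3 study, the intention to treat will be the primary approach".

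Three design features bear on who becomes a recipient:

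- Consent is sought once the village's arm is known (sections 3.1 and 5.1).
- Blinding is stated to be impossible (section 5.1).
- Use of medication outside the safe list excludes a person from BE-PEP only, and that person may be given SDR-PEP instead (section 4.2).

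The supplied SAP covers phase 2 only.

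**The concern.** The protocol accepts that age matters for this comparison, but controls it only with a lower cut-off. Nothing in the documents says that risk is flat from 5 years upward.

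Randomization of villages balances their populations on average. It does not balance subsets that form afterwards, through consent given with knowledge of the regimen and through an exclusion that works in one arm. In arm 1, a person on off-list medication leaves the BE-PEP group; a similar person in arm 2 stays among the SDR-PEP recipients. If such people differ in age from the rest, the two recipient groups differ in age mix. The village random effect cannot absorb that shift, because it runs with the regimen. Pairing does not address it either: clusters are paired on island, former PEOPLE arm and prevalence (section 4.4).

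At stake is the primary incidence rate ratio (IRR). A larger sample would not shrink a bias of this kind.

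**Working it through.** **1. The plan's own figures (section 4.3).** Analysable people per cluster: 2,819 × (1 − 0.27) × 0.83 = 1,708. Hayes-Bennett formula, pair-matched, alpha taken as two-sided (sidedness is not stated), p0 = 0.0033, p1 = 0.00165, km = 0.4, n = 1,708, power 90%:

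c = 2 + (1.960 + 1.282)² × [p0(1 − p0)/n + p1(1 − p1)/n + km²(p0² + p1²)] / (p0 − p1)²

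= 2 + 10.507 × (1.926 + 0.964 + 2.178) × 10⁻⁶ / (2.7225 × 10⁻⁶) = 21.56, so 22 per arm. This matches the plan, as does 44 × 1,708 = 75,152.

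Expected cases: 22 × 1,708 = 37,576 per arm; 37,576 × 0.0033 = 124 under SDR-PEP and half that, 62, under BE-PEP. That is enough for a few extra main-effect parameters. Adding covariates does not alter the stated cluster count.

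**2. Bias formula.** Let one age group have RR times the risk of the rest, with share pS among SDR-PEP and pB among BE-PEP recipients. The unadjusted IRR is multiplied by

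[1 + pB(RR − 1)] / [1 + pS(RR − 1)].

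**3. Illustration.** All shares and risk ratios here are assumed; the documents give neither. With pS = 40%:

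| pB | RR 1.5 | RR 2 | RR 3 |
|---|---|---|---|
| 40% | 1.000 | 1.000 | 1.000 |
| 38% | 0.992 | 0.986 | 0.978 |
| 35% | 0.979 | 0.964 | 0.944 |
| 30% | 0.958 | 0.929 | 0.889 |

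A true IRR of 0.50 would read between 0.444 (0.50 × 0.889) and 0.496 (0.50 × 0.992). If the under-represented group has the lower risk instead (RR replaced by 1/RR), the same unequal shares give factors from 1.008 to 1.091.

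**4. What uptake such shifts require.** The only acceptance figure used in planning is a single overall one: "the proportion of eligible participants that agreed to take PEP, which in the PEOPLE trial was 83" per cent. Hold every other group at 83% and let the group's share of eligible people equal pS. The acceptance needed in that group under BE-PEP is

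a = pB(1 − pS) × 0.83 / [pS(1 − pB)].

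- 40% to 38%: a = 76%
- 40% to 35%: a = 67%
- 40% to 30%: a = 53%
- 30% to 20%: a = 48% (IRR factor at RR 2: 1.20/1.30 = 0.923)
- 15% to 10%: a = 52% (IRR factor at RR 2: 1.10/1.15 = 0.957)

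The larger shifts thus need acceptance in one age group to fall to about half.

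**5. A 10-point drop, 83% to 73%, in a group with RR 2.** Then pB = 0.73 pS / [0.73 pS + 0.83(1 − pS)].

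- pS = 15%: pB = 13.4%, factor 1.134/1.15 = 0.986
- pS = 30%: pB = 27.4%, factor 1.274/1.30 = 0.980
- pS = 40%: pB = 37.0%, factor 1.370/1.40 = 0.978

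**The case against.** The strongest reply is that the documents do not show any difference in age mix. That is correct. A reader might infer that the regimens are likely to be accepted differently across ages, but no passage says so, and 83% is one overall figure from PEOPLE, not broken down by age or regimen. A reader might also point to the tablet burden of BE-PEP. That is weak: 20 mg dispersible tablets are provided in phase 3 (sections 6.1 and 6.5), the 20 to under 30 kg band receives 400 mg (section 5.1), and inability to swallow tablets is a phase 2 exclusion missing from the phase 3 list. That off-list medication varies with age is likewise an assumption.

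Sex has no stated basis as a confounder. No passage says that risk or uptake differs by sex, and the pregnancy and breastfeeding exclusion applies to both regimens.

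The age and weight restriction can be defended as removing people who could appear only among SDR-PEP recipients. It does that, but it does not deal with age differences above the limit.

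The village-level analysis in section 9.3.2 includes everyone, so uptake selection does not operate there. That stands, and it limits the point to 9.3.1.

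A phase 3 SAP may add covariates; section 9 makes the SAP binding, and none for phase 3 was supplied. Section 9.1 plans tests of baseline imbalance but attaches no adjustment to them, and choosing covariates after seeing such tests is what prespecification avoids. The remark in the annex that age subgroups would be underpowered concerns subgroup effects, not a main-effect covariate.

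**Conclusion.** The point holds as a possible, unquantified confounding of the primary estimate, not as a demonstrated bias. What the documents establish is a recipients-only comparison formed after open allocation, an exclusion that acts on BE-PEP alone, a statement that risk varies with age, and no age term in any description of the model.

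Under the assumed inputs the effect is modest: a factor of roughly 0.89 to 0.99, or 1.01 to 1.09 in the other direction, and 0.98 to 0.99 for a 10-point drop in acceptance in one group with twice the risk. With equal age mix it is nil. Against a target IRR of 0.50 this would not by itself create or erase the planned effect, but it would shift the estimate.

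It would be wrong to infer that age adjustment makes the recipients-only contrast equivalent to a randomized one. Selection on medication use, health or willingness would remain. The intention-to-treat statement in section 9.1 and the analysis set in 9.3.1 still have to be reconciled.

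**What to change.** In section 9.3.1 and the phase 3 SAP, before any analysis, including the interim analysis in section 9.3.3:

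- Prespecify age at first PEP as a fixed effect, in bands (for example 5-14, 15-29, 30-49 and 50 years or more) or as a spline. Add sex as a conventional covariate.
- Carry into 9.3.1 the distance to nearest index case that the synopsis and section 3.1 already promise.
- Report the model without age and sex as a sensitivity analysis.
- Add a sensitivity analysis by allocated arm of everyone meeting the BE-PEP age and weight limits, whether or not they took PEP, in line with the approach named in section 9.1.

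Adjustment in section 9.3.2 is optional; there it would address chance imbalance only.

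The cost is a few lines of text. Age is needed to determine PEP eligibility (section 4.2), and section 11.1 lists demographic data for phase 3. Section 11 names an "Access database with barcode, name, age and gender of each participant enrolled", but for the baseline survey, so confirm that the phase 3 database carries sex as well.

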The total enrolment to date in the PEOPLE trial in Comoros has been approximately 86,000. Out of 15,569 persons eligible for PEP in 2019, 12,101 (83.1%) actually took PEP. A preliminary analysis based on data for the second year (2020) shows an incidence of approximately 1.1 per 1,000 (96 new cases). In a Poisson model controlled for differences in baseline prevalence and with village nested in island as random effects to control for contextual confounding, we found incidence rate ratios of 1.23, 0.78 and 0.89 when comparing respectively arms 2, 3 and 4 to arm 1, the comparator arm. None of these associations was statistically significant ($p \geq 0.70$). At individual level the effect of PEP controlled for distance to nearest index case was a borderline statistically significant reduction in risk of leprosy, with an incidence rate ratio of 0.48 (95% confidence interval 0.21-1.13).

Based on the individual effect of SDDR-PEP and taking into account the fact that less than two out of three years of follow-up have passed, the associations at study arm level might still become more pronounced but we do already want to test a stronger PEP regimen making use of the established set up. The regimen we intend to test is a combination of rifampicin and bedaquiline, hereafter referred to as 'Bedaquiline enhanced post exposure prophylaxis' or BE-PEP. Rifampicin will be provided at a dose of 10 mg/kg, the WHO standard, i.e. 600 mg for an adult. Bedaquiline will be provided at a dose of 800 mg for an adult, double the daily dose used in treatment of rifampicin resistant tuberculosis.[6] Based on pharmacological considerations and pre-clinical studies we expect this regimen to have a synergistic action against *M. leprae*. BE-PEP will be administered as a single dose, repeated after four

weeks only for household contacts, as preliminary data from the PEOPLE trial show that their residual risk is still up to three times higher when compared to the rest of the population.

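### Phase 3 sample size (Protocol 4.3): the 83% uptake does not match its own counts, 2,850 should read 2,819, and the village-level power of about 90% matches the recipients-only cluster size rather than the examined population

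*Protocol*

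**What the plan says.** The Protocol Synopsis reports uptake in the PEOPLE trial: "Out of 15,569 persons eligible for PEP in 2019, 12,101 (83.1%) actually took PEP". Section 4.3 uses that figure as an input, describing it as "the proportion of eligible participants that agreed to take PEP, which in the PEOPLE trial was 83" per cent.

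Section 4.3 then builds the primary calculation. It states that "The mean population size of the villages targeted is 2,819", removes the 27% who are below the BE-PEP age or weight limits, applies the uptake, and concludes: "Thus on a population of 2,850, only 1,708 will effectively be available for analysis". On the between-cluster coefficient of variation, "in the BE-PEOPLE trial we assume a slightly higher Km, 0.4". With a 3-year control risk of 0.0033, a 50% reduction in recipients, alpha 0.05 and 90% power, it asks for 22 clusters per arm and 75,152 subjects.

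For the secondary, village-level objective the section says that "the entire population examined will be considered in the analysis" and that, at 1.1 per 1,000 per year, "and a 50% reduction is achieved with BE-PEP, the available sample size would provide a power of approximately 90% over a three-year follow-up period". It names no cluster size, k or matching for this figure. Section 9.3.2 confirms that the village-level analysis includes people who received no PEP or were ineligible. The SAP covers phase 2 only and adds nothing here.

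**The concern.** Three things do not fit. The uptake percentage disagrees with its own counts by more than five points, and it feeds the primary sample size. The section uses two different base populations for the same product. And the village-level analysis has a larger population per cluster than the primary analysis, with the same number of clusters and the same 50% effect, yet its stated power is the same.

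The last point matters most. The Protocol's rationale (section 1.2) is that a stronger regimen is needed to affect transmission, and the village-level comparison is where that would show. A reader should be able to see which village-level effect the trial can detect. The printed figure does not say. It also takes over the recipient-level effect without comment, although many residents will not take BE-PEP.

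**Working it through.** **1. Uptake.** 12,101 / 15,569 = 0.777. The printed 83.1% would follow from 12,101 / 14,569 = 0.831, so a single wrong digit in the denominator is possible.

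**2. Base for 1,708.**
- 2,819 × 0.73 × 0.83 = 1,708.
- 2,850 × 0.73 × 0.83 = 1,727.
- 124,035 / 44 = 2,819, and 44 × 1,708 = 75,152.

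Everything downstream uses 2,819, so 2,850 is the stray figure.

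**3. Reproducing the primary figure.** The section cites the Hayes-Bennett method. For proportions:

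c = a + (z₀.₉₇₅ + z_power)² × [p0(1−p0)/n + p1(1−p1)/n + k²(p0² + p1²)] / (p0 − p1)²

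Here a = 1 for unmatched and a = 2 for pair-matched clusters. Inputs are p0 = 0.0033, p1 = 0.00165 and k = 0.4. Alpha is taken as two-sided because the section does not say. Both values of a are shown because clusters are randomised in 22 pairs (4.4), while the model in 9.3.1 has no pair term.

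The fixed parts are k²(p0² + p1²) = 2.178 × 10⁻⁶ and (p0 − p1)² = 2.7225 × 10⁻⁶. The binomial part is 0.0049364 / n.

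For n = 1,708 the bracket is 2.890 × 10⁻⁶ + 2.178 × 10⁻⁶ = 5.068 × 10⁻⁶. This gives c = 21.6 matched (the printed 22) and 20.6 unmatched. Power with 22 per arm is 90.6% matched and 91.9% unmatched, so the primary figure reproduces.

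If the uptake counts are right, n = 2,819 × 0.73 × 0.777 ≈ 1,599, and the total is 44 × 1,599 ≈ 70,400. Then c = 22.3 matched and 21.3 unmatched, and power with 22 per arm is 89.5% and 90.9%.

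**4. Village-level power for a 50% reduction.** Power = Φ(√[(22 − a)(p0 − p1)² / bracket] − 1.96). For n = 2,819 the bracket is 1.751 × 10⁻⁶ + 2.178 × 10⁻⁶ = 3.929 × 10⁻⁶. The square root is 3.72 matched and 3.81 unmatched.

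| Persons per cluster | Matched | Unmatched |
|---|---|---|
| 1,708 (recipients only) | 90.6% | 91.9% |
| 2,819 (mean cluster, all examined) | 96.1% | 96.8% |
| 2,472 (unequal clusters, all examined) | 95.1% | 95.9% |
| 1,787 (unequal clusters, 72.3% examined) | 91.3% | 92.5% |

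The last two rows allow for cluster-size imbalance. Section 4.3 gives 34 PEOPLE villages with about 73,000 people (mean 2,147) and new villages with about 51,000 people in 10 clusters (mean 5,100). The harmonic mean of these two groups is 44 / (34/2,147 + 10/5,100) = 2,472. The 72.3% is 62,266 screened of 86,160 under follow-up in one PEOPLE round (section 1.1), and 2,472 × 0.723 = 1,787.

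**5. Detectable village-level reduction, matched.** With n from 2,819 down to 1,787, 90% power needs a reduction of 44.5-49.0%, and 80% power needs 39.2-43.2%.

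**6. Illustration of dilution.** This assumes a 50% recipient effect relative to SDR-PEP, one fully covered round and no indirect effect. BE-PEP takers are then 0.73 × 0.777 = 57% to 0.73 × 0.83 = 61% of residents. The village-wide reduction depends on who else gets leprosy:
- Equal risk in everyone: 0.5 × 0.57 to 0.5 × 0.61, or 28-30%.
- No cases in ineligible children, and non-takers at the same risk as SDR-PEP takers: 0.5 × 0.777 to 0.5 × 0.83, or 39-41.5%.
- No cases in ineligible children, and takers at 0.48 times the risk of non-takers (the rate ratio in the Synopsis): 0.5 × 0.48u / (0.48u + 1 − u), with u = 0.777 to 0.83, or 31-35%.

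**The case against.** The best defence is that "and a 50% reduction is achieved with BE-PEP, the available sample size would provide a power of approximately 90% over a three-year follow-up period" is conditional, approximate and not far off. It concerns the population examined, not all residents, and clusters are unequal. With both allowed for, matched power is 91.3%, which can fairly be called about 90%. That stands as far as it goes: documented inputs can bring the figure close to 90%. But the section describes no such calculation. Its own method uses the mean cluster size, and the one documented size that gives 90.6-91.9% under that method is the recipients-only 1,708. The low end is itself cautious: 1.1 per 1,000 is a rate over everyone under follow-up (96 / 86,160), here applied to the screened fraction. Also, section 4.2 counts anyone screened at least once in four years, so more than 72% should be examined.

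The error is also conservative under its own 50% condition, which is true.

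On the 50% itself, the Protocol does hypothesise an effect on transmission (Synopsis and section 1.2), so a village-wide effect beyond direct protection is not excluded. That is fair. What is missing is a statement that the 50% depends on it.

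Finally, the uptake discrepancy may be only a misprinted denominator, in which case 1,708 and 75,152 stand. That is also fair, and the documents do not settle it.

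**Conclusion.** The point holds as a minor correction. The uptake count and percentage conflict (77.7% against 83.1%), 2,850 should be 2,819, and the village-level power was not obtained by the section's method on the population it names. That method gives 96-97%, or about 91-96% with unequal clusters and 72-100% examined. This rests on 22 clusters per arm, k = 0.4, a 3-year risk of 0.0033 and two-sided alpha 0.05.

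A reader might go further in three ways that the documents do not support:

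- That the primary analysis is underpowered and needs more clusters. Even if the counts are right, power with the planned 44 clusters is 89.5% matched or 90.9% unmatched.
- That true uptake was 77.7%. The documents show a conflict, not which number is wrong.
- That the village-level comparison is badly underpowered because of dilution. The 28-41.5% range depends on unstated risks in ineligible children and in eligible people who take no PEP. The 0.48 comes from a double rifampicin dose and has an interval of 0.21 to 1.13. Later PEP rounds or reduced transmission would raise the village effect.

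What can be said is narrower: a 50% effect in recipients would not by direct protection alone give 50% village-wide, so the 50% is an added assumption.

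**What to change.** Reconcile the count and percentage in the Synopsis. If the counts stand, restate about 1,599 per cluster, about 70,400 in total and primary power of about 89.5% (matched) to 91% (unmatched), keeping 44 clusters. If 83.1% stands, correct the counts and keep 1,708 and 75,152. Either way, change 2,850 to 2,819.

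Recompute the village-level power on the examined population, naming the cluster size, its variation, k, the sidedness of alpha and whether matching is used. Expect roughly 91-96% for a 50% reduction. Add the detectable reductions: about 44-49% for 90% power and 39-43% for 80% power, matched.

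State that the 50% is a village-wide assumption that direct protection of recipients alone would not deliver. Give any coverage-based dilution only as an illustration, with its assumptions stated, including the risk in eligible people who take no PEP.

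The cost is text and a short recalculation. No clusters or participants are added. The secondary power statement will depend more visibly on its assumptions.
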